13.5 Reporting procedures

13.5.1 Participating site responsibilities

The PI (or delegated medically qualified doctor from the trial team) should sign and date the SAE CRF to acknowledge that they have performed the seriousness and causality assessments. Investigators should also report SAEs to their health boards or trust in accordance with local practice.

A completed SAE form for all events requiring immediate reporting should be submitted via fax or email to the CTR within 24 hours of knowledge of the event. A separate form must be used to report each event, irrespective of whether or not the events had the same date of onset.

The participant will be identified only by trial number, month or year of birth and initials. The participant's name (or any other personal identifier) should not be used in any correspondence. It is also required that sites respond to and clarify any queries raised on any reported SAEs and report any additional information as and when it becomes available through to the resolution of the event. Additionally, CTR/pharmaceutical companies may request additional information relating to any SAEs/SARs and the site should provide as much information as is available to them to resolve these queries.

Serious Adverse Event (SAE) email address:

[contact]
SAE [contact]

SAEs should be reported from the time of signature of informed consent, throughout the treatment period up to, and including the participant's final follow-up visit (12, 24 or 36-months) or 30 days after withdrawal from trial treatment (whichever is soonest). SARs (such as long-term side effects of trial treatment under investigation) should continue to be reported until the end of follow-up as defined in the protocol (page 44).

SAEs should be graded using the National Cancer Institute (NCI) CTCAE Version 5.0 (https://ctep.cancer.gov/protocoldevelopment/electronic_applications/docs/CTCAE_v5_Quick_Reference_5x7.pdf).

An SAE form should contain at least the minimum information:

- Full participant trial number
- An Adverse Event / Adverse Reaction
- IMP or trial intervention
- A completed assessment of the seriousness, and causality as performed by the PI (or another appropriately medically qualified doctor registered on the delegation log)

If any of these details are missing, the site will be contacted and the information must be provided by the site to the CTR within 24 hours.

AEs will **not** be recorded in this trial. All such non-serious events, whether expected or not, should be recorded in the patient medical notes as per routine procedures.

13.5.2 The CTR responsibilities

Following the initial report, all SAEs should be followed up to resolution wherever possible, and further information may be requested by the CTR. Follow-up information must be provided on a new SAE form

Once an SAE is received at the CTR, it will be evaluated by staff at the CTR and sent to the CI (or their delegate) for an assessment of expectedness.

Investigator reports of suspected SARs will be reviewed immediately and those that are identified as SUSARs are reported to the MHRA and Main Ethics.

13.6 SUSAR reporting

North Bristol NHS Trust is undertaking the duties of trial Sponsor and has delegated to the CTR the responsibility for reporting SUSARs and other SARs to the regulatory authorities (National Competent Authorities (NCAs) and relevant ethics committees) as follows:

- SUSARs which are fatal or life-threatening must be reported to the MHRA and REC within 7 calendar days of receipt at the CTR.
- SUSARs that are not fatal or life-threatening must be reported to the MHRA and REC within 15 days of receipt at the CTR.
- If the report is incomplete then additional follow-up information should be reported within a further 8 calendar days of submitting the initial report, for all fatal and non-fatal, life-threatening and non-life-threatening.

Any additional, relevant information must be reported within a further 15 days.

13.7 Unblinding for the purposes of SUSAR reporting

Not applicable as the drug allocations are not blinded.

13.8 Safety reports

A list of all SARs (expected and unexpected) will be reported annually to the MHRA REC and trial sponsor in the form of a Development Safety Update Report (DSUR). This report must be submitted within 60 days of the anniversary of the MHRA CTA approval date.

The CTR will report a list of all SARs (expected and unexpected) and any other safety recommendations to all PIs annually throughout the trial. This frequency may be reviewed and amended as necessary. This reporting will be done via the Investigator safety report (ISR).

13.9 Contraception and pregnancy

13.9.1 Contraception

While clinical studies suggest that aspirin doses up to 100 mg/day appear safe for restricted obstetrical use under specialised monitoring, there is no clinical data on clopidogrel exposure during pregnancy, making its use inadvisable. Similarly, the safety and efficacy of rivaroxaban in pregnant women are unestablished, and animal studies have shown reproductive toxicity.

People of childbearing potential entering into this trial must agree to use a highly effective method of contraception preferably with low user dependency for at least 7 days after the last dose of clopidogrel, aspirin and clopidogrel, or aspirin and rivaroxaban (based on section 4.4 of the drug SmPCs and the NICE Clinical Knowledge Summary guidance on the discontinuation of clopidogrel and rivaroxaban before surgery for people with a high risk of bleeding (33,34). A highly effective method of contraception is considered as having a failure rate of less than 1% per. Some acceptable contraception methods are listed below;

- combined (oestrogen and progestogen-containing) hormonal contraception associated with inhibition of ovulation:
 - o oral
 - o intravaginal
 - o transdermal
- progestogen-only hormonal contraception associated with inhibition of ovulation
 - oral
 - injectable
 - o implantable*
- intrauterine device (IUD)*
- intrauterine hormone-releasing system (IUS)*
- bilateral tubal occlusion*
- vasectomised partner*
- sexual abstinence is defined as refraining from heterosexual intercourse during the entire period of risk associated with the trial treatments.

N.B. periodic abstinence (calendar, symptothermal, post-ovulation methods), withdrawal (coitus interruptus), spermicides only, and lactational amenorrhoea method (LAM) are not acceptable methods of contraception.

*These contraception methods are considered to be low user dependency.

13.9.2 Pregnancy reporting whilst participating in the trial

Pregnancy, or the pregnancy of a partner occurring whilst participating in the trial, is not considered an SAE, however, a congenital anomaly or birth defect is. Other cases (e.g. termination of pregnancy without information on congenital malformation, and reports of pregnancy exposure without outcome data) should not normally be reported as such. When pregnancy occurs in a trial, either in a female participant or the female partner of a male participant, this should be followed up until at least the end of pregnancy, whether that is a live birth, abortion etc. Without follow-up of the pregnancy, it would not be possible for the CTR to know if a congenital anomaly or birth defect occurred, and therefore if there was an SAE that must be included in the safety evaluation of the IMP. Information on pregnancy in a trial participant will be captured on the CTR Pregnancy Report Form supplied to sites by the CTR.

Sites should report pregnancy occurring within SAE reporting periods stipulated in the trial protocol (for example, some trial protocols may state that SAEs should be reported during the trial treatment period and up to 30 days after the last date of treatment, this timeline would also apply to the reporting of pregnancies). Congenital anomalies or birth defects are considered an SAE and so these events must also be reported to the CTR on a trial-specific SAE form. Congenital anomalies or birth defects related to the IMP and unexpected with respect to the IMP Reference Safety Information (RSI) must be submitted by the CTR within expedited SUSAR time frames (7 or 15 days) to the MHRA, relevant REC and the drug manufacturer of the IMP (to comply with any contractual agreement).

13.10 Urgent Safety Measures (USMs)

An urgent safety measure (USM) is an action that the Sponsor, CI or PI may carry out to protect the subjects of a trial against any immediate hazard to their health or safety. Any USM relating to this trial must be notified to the MHRA and Research Ethics Committee immediately by telephone, and in any event within 3 days in writing, that such a measure has been taken. USMs reported to the CTR will be handled according to CTR processes.

14 Statistical considerations

14.1 Randomisation

Within 10 days of the endovascular procedure being performed, participants will be individually allocated in a 1:1:1 ratio to one of the initial three trial arms: (1) clopidogrel alone, (2) aspirin plus clopidogrel or (3) aspirin plus low-dose rivaroxaban for up to 36 months. Covariate-adaptive randomisation will be used to minimise the imbalance of key covariates with a random element apply to reduce the risk of subversion. These key covariates are:

- target artery (including iliac plus common femoral endarterectomy, iliac plus femoropopliteal, femoropopliteal, femoropoplital plus tibial, tibial, Iliac and tibial, hybrid with common femoral endarterectomy)
- trial site
- antiplatelet loading at the time of procedure (yes/no)

If one arm is dropped due to futility after the interim analysis (see Section 15.1.1.), the randomisation ratio will be adjusted to 1:1 between the two remaining arms.

The randomisation procedure will be implemented via a web-based remote system (available 24 hours a day) with telephone back-up as described in Section 9.5.2. Full details will be provided in a separate randomisation protocol.

14.2 Blinding

The CLARITY trial does not use blinding of patients or clinicians. The statistician will perform the primary analysis blind to allocation.

14.3 Sample size

We aim to recruit 1239 participants over 36 months and follow them up for a maximum of 36 months if recruited earlier in the trial, or a minimum of 12 months if recruited later. Assuming a 12-month event-free survival rate of 65.0% in the clopidogrel alone arm; an increase to 75.6% in at least one of the intervention arms, corresponding to a hazard ratio of 0.65 (10,11,14,35), a dropout/loss to follow-up rate of 8%/year (unpublished BASIL 3 data); a two-group log-rank test of equal exponential survival with a two-sided alpha of 2.5% (accounting for the three-arm design) and 90% power requires 387 primary outcome events (157 expected in the clopidogrel alone arm, 115 in each of the combination arms) to be observed (BASIL 3 data provided by Chief Investigator). Given the 36-month recruitment period (assuming 25%, 35% and 40% recruitment in the first, second and third year, respectively) and a maximum follow-up period of 36 months, this translates into 413 participants per arm, or 1239 in total (calculated with ART version 1.1.0 using Stata version 17.0) (36,37).

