12.2 Follow-up

Follow-up assessments will occur at specific intervals: within 2 months of the endovascular procedure (+ 1-month window), at 6 months (+/- 2-month window) and 12 months (+/- 2-month window) after randomisation. These assessments can be conducted in person (at a 2-month routine clinical appointment) or by telephone/video call/email communication. Early recruits will have additional follow-ups at 24 months (+/- 2-month window) and 36 months (+/- 2-month window) after revascularisation, if they reach those timepoints. The duration of follow-up will depend on the timing of entry into the trial, with follow-up ending either at 36, 24 or 12 months after revascularisation. The follow-up period will end 12 months (+/- 2-month window) after the last recruited participant has been randomised and initiates medication (at completion of their 12 follow-up assessments).

Participants will be sent two reminders by either the central research team or the research nurse via their chosen method of contact (text, email, post) to maximise follow-up.

Around 3 attempts will be made to contact the participant at each follow-up according to their preferred method of contact. If it is not possible to contact participants, a relative/carer may be contacted as an alternative. If all contact attempts are unsuccessful, a questionnaire booklet may be posted to the participants for them to complete and return. If a routine in-person outpatient visit is scheduled for clinical reasons within the follow-up visit windows, the follow-up questionnaires may be completed in-person, and/or clinical information collected at this visit may be used for follow-up assessments. Site staff will ensure, to the best of their knowledge, that participants are still alive before any contact attempts are made, by checking all local patient management systems available to them e.g. Spine data (England), Welsh Clinical Portal (Wales).

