15.1 Main analysis

The final analysis will be performed after the end of the trial follow-up period, which is 48 months after the start of recruitment. Baseline demographic and clinical characteristics will be summarised descriptively by arm.

The primary analysis will be an intention to treat (ITT), including all randomised participants with non-zero follow-up time.

For the composite primary outcome (time from randomisation to the first occurrence of any element of the composite), a two-level Cox proportional hazards regression model will be fitted to estimate hazard ratios, including fixed effects for allocation and random effects to model heterogeneity between sites. Participants are censored at the end of the planned follow-up period (36 months), at

the end of the trial follow-up period, or (in case of dropout) at the time of their last follow-up, whichever occurs first. Regression analysis results will be presented as point estimates with confidence intervals and p-values from a log-rank test, and Kaplan-Meier curves of cumulative event rates at 36 months (31,32) will be generated to compare arms over time.

Primary estimand

Primary outcome question: In patients following endovascular intervention for CLTI, what is the event-free survival time of the three commonly used antithrombotic regimens (clopidogrel; aspirin plus clopidogrel; aspirin plus low-dose rivaroxaban), for those with a non-zero follow-up time?

The primary estimand is described by the following attributes:

- Population: Adults who are first time in CLARITY trial undergoing percutaneous or hybrid endovascular intervention for CLTI of the lower limbs, with atherosclerosis as the cause of CLTI, and with non-zero follow-up time.
- **Endpoint**: The clinical effectiveness endpoint is a composite event-free survival time examined over the trial duration. These events included acute limb ischaemia, major lower limb amputation, myocardial infarction, ischaemic stroke, and all-cause mortality. Participants are censored at the end of the planned follow-up period (36 months), at the end of the trial follow-up period, or (in case of dropout) at the time of their last follow-up, whichever occurs first.
- **Treatment condition**: Clopidogrel, aspirin plus clopidogrel, and aspirin plus low-dose rivaroxaban, regardless of discontinuation or initiation of the antithrombotic regimens.

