15.1.1 Sub-group & interim analysis

A planned interim analysis of the co-primary outcomes will be conducted when 60% of the planned maximum number of primary outcome events have been observed. The interim analysis will compare each of the combination arms against the clopidogrel-only arm (which has the lowest predicted clinical effectiveness) using futility-stopping criteria based on conditional or predictive power which leads to minimal overall power loss. These criteria will be finalised during the trial set-up phase and fully specified in the SAP.

If the futility of the clopidogrel-only arm is shown in at least one of the two comparisons, the trial will continue with the two combination arms only. Participants in the futile arm will continue with the allocated drug and will be followed up until the end of the trial. If all three arms continue through to the final analysis, each of the combination arms will be compared to clopidogrel only, each at 2.5% alpha. If only one is significantly better, it will be declared the most effective. If both combination therapy arms are significantly better, they will then be compared against each other using the full 5% alpha, thus ensuring strong control of the familywise type I error rate.

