At a local level, we will interact with and promote research findings through wider NHS Trusts and the NIHR Clinical Research Networks. Nationally, we will engage with NICE, the Vascular Society of Great Britain and Ireland, the British Society of Interventional Radiology, the British Society for Endovascular Therapy, the Vascular Anaesthesia Society of Great Britain and Ireland, and the Vascular and Endovascular Research Network, as well as relevant charities such as the Douglas Bader Foundation. We anticipate the results directly impacting clinical antithrombotic guidelines, which to date do not

include recommendations regarding optimal antiplatelet/anticoagulant usage post-endovascular intervention.

26 Milestones

The CLARITY trial is a five-year trial with the following project timetable:

- Month 1-8: Trial and site set-up, contracts, regulatory approvals.
- Month 9-17: Internal pilot (assessed by progression criteria) and recruitment. Assess the acceptability of intervention and trial processes.
- Month 18-54: Continuation of RCT recruitment, follow-up and data collection, and interim analysis (when 60% of primary outcome events have been observed).
- Month 55-60: Data cleaning, statistical analysis, preparing HTA report, draft papers, and dissemination activities.

27 References

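### Section 14.3's 387 events and 90% power match 413 per arm only if follow-up ends at month 36, not at the planned month-48 analysis; the error is conservative, but the interim trigger inherits it

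*Protocol*

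**What the plan says.** Section 14.3 (Sample size) assumes 65.0% event-free survival at 12 months on clopidogrel alone, 75.6% on a combination (hazard ratio 0.65), 8% loss per year, two-sided alpha of 2.5% and 90% power. Recruitment takes 36 months, split 25/35/40% by year. From these inputs the design "requires 387 primary outcome events (157 expected in the clopidogrel alone arm, 115 in each of the combination arms) to be observed", which the section turns into 413 per arm, 1,239 in all.

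The same section says the trial will recruit participants and "follow them up for a maximum of 36 months if recruited earlier in the trial, or a minimum of 12 months if recruited later". Section 15.1 agrees: "The final analysis will be performed after the end of the trial follow-up period, which is 48 months after the start of recruitment".

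Section 15.1.1 says the interim analysis "will be conducted when 60% of the planned maximum number of primary outcome events have been observed". It gives no count, and 387 is the only planned total in the protocol.

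Two other places describe when follow-up ends. Section 12.2 describes the duration "with follow-up ending either at 36, 24 or 12 months after revascularisation", and also closes follow-up 12 months after the last randomisation. Section 26 (Milestones) has "Month 18-54: Continuation of RCT recruitment, follow-up and data collection, and interim analysis", with the pilot and recruitment starting in project month 9.

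**The concern.** A control event rate of 35% per year with 12 to 36 months of follow-up should produce many more than 157 events among 413 control participants. Twelve months for everyone, and no more, would already give about 139. So the stated event count appears to belong to a shorter trial than the one described.

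Two things are at stake. First, the funder, ethics committee and data monitoring committee are told the trial has 90% power for a hazard ratio of 0.65, when the planned calendar gives a different figure. Second, the interim is a percentage of a planned event total. If that total is wrong, the interim falls at a different share of the final information from the 60% stated. A futility rule based on conditional or predictive power depends directly on that share.

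**Working it through.** **Inputs (all Section 14.3 unless stated).**
- Control hazard: λc = −ln 0.65 = 0.4308 per year.
- Combination hazard: λt = 0.65 × 0.4308 = 0.2800, giving exp(−0.2800) = 75.6% at 12 months, as stated.
- Loss hazard: δ = −ln 0.92 = 0.0834.
- Entry uniform within each year, weights 0.25, 0.35, 0.40; 413 per arm.

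**Formula.** For follow-up t, P(event) = λ/(λ+δ) × [1 − exp(−(λ+δ)t)], averaged over entry time.

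For the control arm λ+δ = 0.5142 and λ/(λ+δ) = 0.838. The bracket averages 0.218 for follow-up spread over 0–1 years, 0.533 over 1–2 years and 0.720 over 2–3 years. It is 0.786 for exactly 3 years.

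**Step 1: reproduce the protocol's figure (cut at month 36).** First-, second- and third-year entrants have 2–3, 1–2 and 0–1 years.
- Control: 0.838 × (0.25×0.720 + 0.35×0.533 + 0.40×0.218) = 0.380; × 413 = 157.0.
- Combination, same method: 0.277 × 413 = 114.3.
- Total: 157.0 + 2 × 114.3 = 386. Entering loss as a hazard of 0.08 gives 387.

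This matches 157/115/115.

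**Step 2: the planned calendar (month 48, 36-month cap).** First-year entrants have 3 years, second-year 2–3, third-year 1–2.
- Control: 0.838 × (0.25×0.786 + 0.35×0.720 + 0.40×0.533) = 0.554; × 413 = 229.0.
- Combination: 0.417 × 413 = 172.1.
- Total: 229 + 2 × 172 = 573.

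**Step 3: power.** Power = Φ(0.4308 × √(D/4) − 2.2414), with D the events in one pairwise comparison. Required D for 90% is 268 (Schoenfeld) or 276 (Freedman), so the protocol's 157 + 115 = 272 is a sound target.

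| Follow-up rule | Control / each combination | Total | Pairwise D | Power, HR 0.65 |
|---|---|---|---|---|
| Cut at month 36 | 157 / 114 | 386 | 271 | 90.4% |
| Fixed 36/24/12 months by entry year | 201 / 149 | 500 | 351 | 96.3% |
| Cut at month 46 (Section 26) | 220 / 165 | 549 | 385 | 97.6% |
| Cut at month 48 (Section 15.1) | 229 / 172 | 573 | 401 | 98.1% |

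If only one combination arm benefits, the month-48 total is 229 + 229 + 172 = 630; the power of that arm's comparison is unchanged. With 413 per arm at month 48, 90% power is reached at a hazard ratio of about 0.71 (about 0.70 at month 46, 0.69 under the 36/24/12 rule). Getting 157 control events at month 48 would take about 42% loss per year instead of 8%.

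**Step 4: interim.** 60% × 387 = 232 events, expected near month 28 with about 72% recruited.
- Against 573: 232/573 = 40%.
- Against 630: 37% (the count is then reached near month 26).
- Against 500: 46%.

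If 60% is meant of the recalculated total, 0.60 × 573 = 344 events, near month 34 with about 93% recruited.

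**Step 5: timetable.** The start of project month 9 to the end of month 54 is 46 months, against 48 in Section 15.1.

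**The case against.** The strongest reply is that nothing is endangered. About 272 pairwise events do give 90% power, and 1,239 participants will deliver at least that many on the protocol's assumptions. This stands: a reader might infer that the trial is underpowered, and the documents show the opposite.

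A reader might also infer that the futility rule has wrong error rates. The documents do not support that. Section 15.1.1 leaves the criteria to the SAP, which is not at hand, so no rule calibrated to 60% can be examined. As an illustration on assumed values, take a conditional-power threshold of 0.20 under hazard ratio 0.65, applied at 163 pairwise events. If it is calibrated to 272 final events but the trial runs to 401, power falls only from 98.1% to 97.5%. What remains is that the protocol supplies an unclear, and probably wrong, denominator to whoever writes the rule.

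Nor is there a real prospect that the final analysis would be taken at 387 events: no section makes it event-driven, and Section 15.1 already fixes month 48.

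The 36/24/12-month wording in Section 12.2 can be read as a visit schedule, and the two-month gap in Section 26 is a timetable matter. Both need tidying, but neither carries the point. Finally, the match at month 36 suggests that 36 months was entered as total study length, but the software inputs are not shown, so the cause is inference.

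**Conclusion.** The point holds as an internal contradiction in Section 14.3. The 387 events and 90% power do not belong to 413 per arm followed for 12 to 36 months with analysis at month 48. On the protocol's own assumptions that trial expects about 573 events, with a range of about 500 to 630 according to the follow-up rule and how many arms benefit. It has about 96 to 98% pairwise power for hazard ratio 0.65. The direction is conservative.

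The practical consequence is the interim, which would fall at about 40% of the final events (37 to 46% over the same range), not 60%. This rests on reading the planned maximum as 387, which is an inference, though no other number is offered.

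All figures assume exponential survival, 8% annual loss and the stated accrual. Section 11.4's censoring of participants who change antithrombotic for other reasons would lower the counts if applied.

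**What to change.** 1. Rerun Section 14.3 with 36 months' accrual, a 36-month cap per participant and the month-48 cut-off. Restate expected events by arm and either the power for hazard ratio 0.65 or the hazard ratio detectable with 90% power. Say whether one or both combination arms are assumed to benefit. Leave enrolment at 1,239.
2. In Section 15.1.1, state the interim trigger as an event count. Base the conditional or predictive power rule on that count divided by the recalculated final total. The choice is a trade-off: 232 events come near month 28 with about 72% recruited, while 344 come near month 34 with about 93% recruited and little recruitment left to adapt.
3. Align the end of follow-up in Section 12.2 and the project months in Section 26 with Section 15.1.

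The cost is one recalculation and protocol and SAP wording. No extra participants or visits are needed, but it should be settled before the interim.
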